1.5. Schedule of Activities (SoA)

There are additional PK assessments for any pregnant participants who are remaining in the study. See [Appendix 8](#)

Table 3 Schedule of Activities for Patient Study Participants (CAB LA + RPV LA Monthly Administration)

Procedures	Screening ^a	Intervention Period												WD ^o	
		Day 1	Month 1	Month 2	Month 3	Month 4	Month 5	Month 6	Month 7	Month 8	Month 9	Month 10 ^c	Month 11 ^c		Month 12 ^c
Written Informed Consent ^b	X														
Demography	X														
Eligibility Verification	X														
Physical Exam	X														
Medical History	X														
Center for Disease Control and Prevention (CDC) Classification	X														
Randomization for interviews		X													
Rapid Plasma Reagin (RPR)	X														

Procedures	Screening ^a	Intervention Period												WD ^o	
		Day 1	Month 1	Month 2	Month 3	Month 4	Month 5	Month 6	Month 7	Month 8	Month 9	Month 10 ^c	Month 11 ^c		Month 12 ^c
Symptom Directed Physical Exam and Medical Assessment ^d	X	X	X	X		X		X		X		X		X	X
Injection site reaction (ISR) assessment			X	X	X	X	X	X	X	X	X	X	X	X	X
Vital Signs (temperature, blood pressure [BP], heart rate [HR]) ^e	X	X	X	X		X		X			X			X	X
Weight, Height & body mass index (BMI) ^f	X	X	X					X						X	X
HIV Associated Conditions, AE and serious adverse event (SAE) Assessments & Con Meds	X	X	X	X		X		X		X		X		X	X
12-Lead ECG ^g	X														X

Procedures	Screening ^a	Intervention Period												WD ^o	
		Day 1	Month 1	Month 2	Month 3	Month 4	Month 5	Month 6	Month 7	Month 8	Month 9	Month 10 ^c	Month 11 ^c		Month 12 ^c
Clinical and Hematology			X	X		X		X			X			X	X
Pregnancy Testing (U)rine or (S)erum ^h	U	U	U	U	U	U	U	U	U	U	U	U	U	U	U
HIV-1 RNA	X	X	X	X		X		X		X		X		X	X
Plasma sample for storage ^{i,j}		X	X	X		X		X		X		X		X	X
CD4+cell counts	X	X	X	X		X		X			X			X	X
Urinalysis	X														X
Glucose	X														
Prothrombin time (PT)/ partial thromboplastin time (PTT)/ international normalized ratio (INR)	X														X
Oral study product dispensation		X													

Procedures	Screening ^a	Intervention Period													WD ^o
		Day 1	Month 1	Month 2	Month 3	Month 4	Month 5	Month 6	Month 7	Month 8	Month 9	Month 10 ^c	Month 11 ^c	Month 12 ^c	
LA study product administration ^k			X ⁿ	X	X	X	X	X	X	X	X	X	X	X	
Participant Visit Reminder Contact	X	X	X	X	X	X	X	X	X	X	X	X	X	X	
Participant Contact Detail Confirmation	X	X	X	X	X	X	X	X	X	X	X	X	X	X	
Record study visit length ^l			X				X						X		

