Patient Questionnaire			X			X								X	
Selected Patient Interviews (SSI) ^m		X												X	

See footnote "c" for continuation of visit schedule after Month 12, if required. Subjects will continue on study until the CAB + RPV LA regimen is either locally approved and commercially available, the participant no longer derives clinical benefit or meets a protocol-defined reason for discontinuation or until development is terminated.

- A screening visit will be conducted within 21 days of Day 1. However, it is preferred for Day 1 to be conducted as soon as practical after all screening results are available.
- After discussion of risk:benefit, a pregnancy specific ICF addendum must be signed by pregnant participants who wish to remain in the study
- Continue this pattern for visits for the remainder of the study if needed, until commercial CAB + RPV LA is available. For example, Month 13 will be conducted as per Month 10, Month 14 will be conducted as per Month 11, Month 15 will be conducted as per Month 12, Month 16 will be conducted as per Month 10, and so on. The exception to this pattern is that no questionnaires, study visit length collection, or patient interviews will be conducted after the Month 12 visit.
- Physical exams should be conducted as part of normal routine clinical care but data will not be collected in the electronic case report form (eCRF). Medical assessments include any decisions the study staff must make for participant management.
- Measure vital signs after about 5 minutes of rest in a semi-supine position.

- f. Height collected at Day 1 only.
- g. At Screening, ECGs should be performed in triplicate at least 5 minutes apart and following 5 minutes of rest in a semi-supine position. ECG evaluations performed at subsequent visits should be obtained after dosing, preferably 2-4 hours post dosing. ECG at Withdrawal should be performed following 5 minutes of rest in a semi-supine position.

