- h. A (-) urine pregnancy test is required prior to any injection and as required by medical monitor after a treatment interruption. A (+) urine test should be confirmed with a stat serum test. A Serum pregnancy test should be performed at any time pregnancy is suspected by the Investigator and may be used in place of a urine test at the discretion of the investigator. Pregnant participants who remain in the study do not need pregnancy testing during the study, for the duration of their pregnancy. Pregnant participants remaining in the study have additional assessments required, as described in [Appendix 8](#)
- i. Plasma for storage samples are collected for possible future analyses, back-up in cases of loss/damage in transit, geno/pheno analyses for virologic failures or PK in the event of maladministration or virologic failure.
- j. Participants who get pregnant while in study will have additional PK samples for CAB and RPV obtained. See [Appendix 8](#)
- k. Monthly injections are 1 x CAB LA 600 mg IM + 1 x RPV LA 900 mg IM at Month 1. Subsequent injections beginning at Month 2 are 1 x CAB LA 400 mg IM + 1 x RPV LA 600 mg IM. If possible, injections should be spaced approximately 2 cm from one another and from the site of any previous injection and/or any injection site reaction. Bring RPV LA to approximately room temperature prior to injecting. Time and location of injection (right or left) as well as needle length used will be collected in the eCRF. **IM dosing is expected to occur during the month in which the participant's projected visit falls (as according to the Day 1 visit). A dosing window of +0 / -7 days from date of projected visit is stipulated for IM dosing at Month 2 and Month 3. A (+ or -) 7 day window from date of projected visit is stipulated for IM dosing beginning at Month 4. All decisions regarding dose interruption/resumption must be discussed with the medical monitor in advance.**
- l. Length of study visit from arrival until departure from clinic will be evaluated. Time of arrival, time of appointment, and departure times will be recorded in the eCRF.
- m. The first semi-structured interview will be scheduled between Day 1 and prior to Month 1 visit. The end of study SSI will be scheduled within approximately within approximately 4 weeks of their Month 12 study visit.

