To measure patient satisfaction with process (timeliness of visits, length of visit, patient education)	
Patient Survey responses at Month 1, Month 4 and Month 12.
 
Patient SSI responses prior to Month 1 and at Month 12
 
Length of patient visit from arrival until departure from clinic at Month 1, Month 5 and Month 11

Evaluate safety and efficacy measures of CAB+RPV LA	
Proportion of participants with plasma HIV-1 RNA <50 c/mL over time
 
Proportion of participants with confirmed virologic failure (CVF) over time
 
Incidence of treatment emergent genotypic and phenotypic resistance to CAB and RPV in patients with CVF
 
Incidence and severity of AEs and laboratory abnormalities over time
 
Proportion of participants who discontinue treatment due to AEs over time
 
Reported injection site reactions over time
 
Absolute values and changes in laboratory parameters over time

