10.10. Appendix 10: Patient Study Participant Surveys

A survey will be administered to the patient study participants at three timepoints:

- Month 1 visit- at the end of the oral dosing period, prior to receiving the CAB+RPV injection.
- Month 4 visit
- Month 12/ End of Study

Each of the patient surveys will include approximately 40-50 questions and will take about 15 minutes to complete. Patients will be asked to answer the questions at Month 1 based on their current expectations of receiving the CAB+RPV injection, and at the Month 4 and 12 timepoints, based on the current experience receiving the injection.

The following concepts are measured in the patient study participant surveys:

- Acceptability of the CAB+RPV injection (AIM)
- Appropriateness of the CAB+RPV injection (IAM)
- Facilitators and barriers to implementation of the CAB+RPV injection
- Utility of patient specific toolkit resources
- Patient satisfaction with current treatment (HIV-TSQs, HIV-TSQc)

Acceptability and appropriateness will be measured by the Acceptability of Intervention Measure (AIM) and Intervention Appropriateness Measure (IAM), which are constructs validated from the Proctor Framework. Responses are measured using a 5-point Likert scale. ([Weiner, 2017](#))

Additional questions are included to evaluate facilitators and barriers from the patient perspective, and to evaluate the usefulness of the patient specific toolkit resources.

Patient satisfaction will be measured using the validated HIV Treatment Satisfaction Questionnaire (HIV-TSQ), status version (HIV-TSQs), which measures satisfaction with the treatment used in the previous few weeks, and the HIV-TSQ change version (HIV-TSQc), which measures change in satisfaction over time. The HIV-TSQs will be included at all 3 timepoints, while the HIV-TSQc is only measured at Month 12/End of study. ([Woodcock, 2006](#))

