10.12.1. Changes to Study Visits and Study Procedures

- Where site staff resource is constrained due to COVID-19, IM dosing visits may proceed with limited or no other protocol-defined assessments (e.g. lab tests, questionnaires, etc.). If lab tests will be missed for more than one consecutive visit, the medical monitor must be contacted, to provide guidance for safety monitoring.
- For FRP, point of care pregnancy testing should be performed, prior to IM dosing.
- If central laboratory testing cannot be performed at a particular visit, and monitoring for safety is required, tests may be performed at an appropriately authorised/accredited local laboratory (or other relevant clinical facility), if this

can be done within local restrictions on physical distancing. The site should proactively inform the sponsor about such instances. Local laboratory results may be used to inform safety decisions. Results should be retained in source records.

- When on-site visits are reduced, it is important that the investigator continue collecting relevant clinical information, including adverse events, from the participant through alternative means, e.g. by telephone contact.
- There may be cases where the current principal investigator (PI) of a site is indisposed for a period and may need to delegate parts of his/her duties temporarily, e.g. to a sub-investigator. Any such changes should be documented in the site's source records. Any permanent changes in PI should be communicated to the sponsor.
- There may also be circumstances where immediate actions are required by the sponsor and/or investigator, outside of what is contemplated in the protocol, in order to protect a study participant from immediate hazard. Any such measures will be carefully documented and conducted in accordance with the National Competent Authority (NCA)/IRB/IEC regulations.

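### Visit length is timed at one of the two heaviest injection visits (Month 1) and then only at two of the lightest (Months 5 and 11), so part of any fall from Month 1 is built into the schedule

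*Protocol*

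**What the plan says.** Section 3 (and Section 1.2) sets the secondary objective "To measure patient satisfaction with process (timeliness of visits, length of visit, patient education" and gives three endpoints for it: patient survey responses, patient interview responses, and "Length of patient visit from arrival until departure from clinic at Month 1, Month 5 and Month 11". The last is the only one of the three that is not self-reported.

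In Section 1.5, the Table 3 row "Record study visit length" is marked at Months 1, 5 and 11 and nowhere else. Footnote l says "Length of study visit from arrival until departure from clinic will be evaluated" and adds "Time of arrival, time of appointment, and departure times will be recorded in the eCRF". What is timed is the whole visit; no single procedure is timed.

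The Table 3 row "Patient Questionnaire" is marked at Months 1, 4 and 12. Section 10.10 says of the survey: "Each of the patient surveys will include approximately 40-50 questions and will take about 15 minutes to complete". Section 9.4 plans to summarise quantitative data by visit, both as observed values and as change from baseline, for primary and secondary endpoints as appropriate.

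**The concern.** Arrival-to-departure time depends on how the clinic is organised and on what the trial schedules at that visit. If content drops sharply between the first timed visit and the later ones, the time will tend to drop too, even in a clinic whose workflow has not changed.

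This matters because the study is meant to tell clinics what delivering monthly injections demands of them. No visit before Month 1 is timed, so Month 1 is the only possible baseline for this endpoint. A change-from-baseline summary would then be exactly the comparison that mixes content with process. An analysis plan can restrict the comparison, but it cannot recover times that were never recorded.

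**Working it through.** The protocol states no sample size or precision for this endpoint, so there is no planned figure to reproduce. The check is a count of the rows of Table 3 (Section 1.5).

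**Step 1. Scheduled items per injection visit.** Two rows are left out: the one that records visit length, and the interview row, because interviews are scheduled around the visit.

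| Month | 1 | 2 | 3 | 4 | 5 | 6 | 7 | 8 | 9 | 10 | 11 | 12 |
|---|---|---|---|---|---|---|---|---|---|---|---|---|
| Items | 14 | 12 | 5 | 13 | 5 | 13 | 5 | 9 | 8 | 9 | 5 | 14 |

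The timed visits are Months 1, 5 and 11: 14, 5 and 5 items.

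**Step 2. What separates them.** 14 − 5 = 9 items are present at Month 1 and absent at Months 5 and 11:
- symptom-directed examination
- vital signs
- weight and BMI
- scheduled adverse event and concomitant medication review
- chemistry and haematology
- HIV-1 RNA
- stored plasma
- CD4+ count
- patient questionnaire

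Months 5 and 11 share the same five: injection site assessment, pregnancy test, injections, visit reminder and contact check. Blood is drawn at 8 of the 12 injection visits (Months 1, 2, 4, 6, 8, 9, 10 and 12), and not at Month 5 or 11.

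**Step 3. Time that the protocol itself states.**
- Survey: about 15 minutes (Section 10.10), completed at Month 1 before the injection.
- Rest before vital signs: about 5 minutes (Table 3, footnote e).
- Sum: 15 + 5 = about 20 minutes at Month 1 that Months 5 and 11 lack.

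The sum assumes that the two follow one another and do not fill time the patient would have spent waiting anyway. The protocol gives no duration for examination, adverse event review or blood draw.

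**Step 4. Other differences at Month 1.** It is the visit of the last oral dose and the first injections (Sections 1.3 and 6.1), so first-dose handling and staff learning are also mixed into it.

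**Step 5. Which pairs match by Table 3.**
- Month 5 and Month 11: identical; both timed.
- Month 4 and Month 12: differ only in weight (13 and 14 items); neither timed.
- Month 1 and Month 12: same items (14 and 14), apart from the differences in Step 4; only Month 1 timed.

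**The case against.** The strongest reply is that the schedule already contains a sound comparison. Months 5 and 11 have identical content, and they fall on either side of the planned end of facilitation, which is the last enrolled patient's Month 6 visit. That suits a question about whether practice is sustained. This stands. A reader might infer that the endpoint cannot show whether clinics became faster; the documents do not support that, because Month 5 against Month 11 can show it. What it cannot show is the change between the first injections and Month 5, when most learning would be expected.

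Second, the protocol nowhere says that a shorter visit counts as improvement, tests no hypothesis, and places the change-from-baseline sentence under survey data, with details left to the Reporting and Analysis Plan. It is therefore an inference that the fall will be presented as better process. But the same paragraph of Section 9.4 covers secondary endpoints, and the objective names length of visit, so the reading is a natural one to guard against.

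Third, it may be tempting to say that Months 5 and 11 understate the usual visit. Section 2.2 describes routine care as a visit with laboratory tests every 3-6 months, so a lean injection visit may be nearer to ordinary delivery than a visit with blood draws and a survey. Choosing Months 5 and 11 is defensible; the mismatch with Month 1 is the problem.

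Fourth, Section 10.12.1 says "IM dosing visits may proceed with limited or no other protocol-defined assessments" under COVID-19 constraints. A reader might infer that this shortens Months 5 and 11 further. It barely can, since those visits have almost nothing left to drop. It matters more for the content-heavy visits.

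**Conclusion.** The point holds in limited form. The Month 1 to Month 5 and Month 1 to Month 11 changes in visit length are confounded with a scheduled drop from 14 items to 5. About 20 minutes of that rests on the protocol's own durations, under the assumption in Step 3. Any larger figure needs assumed times for examination, review and blood draw, which the protocol does not supply. The expected direction, a shorter visit at Months 5 and 11, does not depend on those assumptions.

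The endpoint is one descriptive item under one secondary objective, and Month 5 against Month 11 remains a valid comparison. This is a cheap improvement and not a fault that undermines the study.

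**What to change.** 1. Mark the visit-length row of Table 3 at Months 4 and 12 as well, and amend the endpoint in Sections 1.2 and 3 to match. Record arrival, appointment and departure times there.
2. Compare only visits with matching content: Month 5 with Month 11; Month 4 with Month 12, which differ only in weight; and Month 1 with Month 12, noting that Month 1 also includes the last oral dose and first injections.
3. State that Month 1 against Month 5 or 11 is not to be read as a change in clinic process.
4. Leave off-site or assessment-reduced COVID-19 visits out of the content-matched comparisons. For an injection given outside the clinic (Section 10.12.3), clinic arrival-to-departure time has no meaning.

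Reporting arrival-to-injection time would not solve the problem, because the Month 1 survey is completed before the injection and so falls inside that interval.

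The cost is three clock times at two visits that already take place: at most 3 × 2 × 135 = 810 further entries if all 135 patients attend both. For visits already held, only items 2 to 4 can still be applied, to the visits that were timed.

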4. STUDY DESIGN

4.1. Overall Design

This study is a single-arm, multicenter, one-year evaluation of the effect of an implementation strategy on the degree of acceptability, appropriateness, feasibility, fidelity, and sustainability of clinic practices to deliver the CAB + RPV LA regimen to appropriate HIV-infected patients. The study will use an implementation study approach at various clinic types (university/hospital, private clinic or public health) to develop a site-specific framework for delivering the CAB + RPV LA regimen which could be adapted for broad utilization upon commercial availability of this regimen.

4.2. Scientific Rationale for Study Design

This time-sensitive proposal will evaluate the implementation of CAB + RPV LA for HIV treatment into University/Hospital, public health clinics, and private practices clinic settings through an implementation Hybrid Type III evaluation. This will be a phase IIIb, qualitative, multicentre study design to evaluate intervention strategies (suite of training and implementation tools as well as short-term facilitation). The clinical effectiveness of CAB + RPV LA will be also captured as a secondary endpoint. A mixed methods approach is proposed where quantitative (surveys) and qualitative (key informant interviews) implementation outcomes are collected, as well as quantitative data to assess clinical effectiveness outcomes. Summative implementation outcome data will be analysed using the Proctor framework and survey questionnaires. The barriers, facilitators, sustainment, fidelity, use of implementation tools, training and patient satisfaction will be analysed using semi-structured interviews from the validated CFIR framework. Sharing best practices and key learnings will be analysed by short-term facilitation calls.

4.3. Justification for Dose

4.3.1. Oral Lead-In Phase

Participants in 209493 will enter the study virologically-suppressed on an oral SOC regimen and will receive oral CAB 30 mg + RPV 25 mg once daily during the oral lead-in phase to confirm tolerability prior to receiving CAB LA + RPV LA injectable treatment.

Oral CAB has been co-administered with oral RPV in several studies. No clinically relevant drug-drug interaction following repeat oral administration of CAB with RPV was observed in healthy subjects in LAI116181 [GlaxoSmithKline Document Number [2011N130484_00](#)]. Oral RPV 25 mg once daily, the approved oral dose of RPV, was administered in combination with oral CAB to HIV-infected participants in the dose-ranging Phase 2b study LAI116482 [(LATTE, (CAB 10, 30, or 60 mg once daily)); GlaxoSmithKline Document Number [2014N216014_00](#)] and 200056 [LATTE-2] (GlaxoSmithKline Document Number [2013N168152_05](#)) with CAB 30mg once daily during the ~4 week oral lead-in phase and in Phase 3 studies 201585 [ATLAS] and 201584 [FLAIR] which are evaluating Q4W dosing of CAB LA + RPV LA.

LAI116482 (LATTE), a Phase 2b, dose-ranging study (randomized 1:1:1: to CAB 10 mg, 30 mg, or 60 mg) evaluated the long-term efficacy and safety of a two-drug, two-class, once-daily combination of CAB + RPV in HIV-infected, treatment-naïve adult participants. Following a 24-week phase of induction of virologic suppression using CAB + 2 NRTIs, the regimen was simplified to a dual regimen, where subjects continued their randomized oral dose of CAB with RPV 25 mg once daily for an additional 72-weeks (total comparative study duration of 96 weeks; [Margolis, 2018], after which one oral CAB dose was selected for progression into the Extension Phase with RPV 25 mg once daily.

Across all dose arms, CAB achieved similar efficacy when co-administered with 2 NRTIs at Weeks 16 and 24, and on dual treatment with RPV at Weeks 48 and 96, respectively (Table 8). Rates of virologic suppression through Week 96 (Maintenance) were numerically higher than the EFV-based comparator regimen.

Table 8 Proportion (95% CI) of Participants with Plasma HIV-1 RNA <50 c/mL at Key Visits - Snapshot (MSDF) Analysis (ITT-E Population) in LATTE

Visit		CAB 10 mg N=60	CAB 30 mg N=60	CAB 60 mg N=61	CAB Subtotal N=181	EFV 600 mg N=47
Week 16 +2 NRTIs	n (%)	54 (90)	50 (83)	53 (87)	157 (87)	46 (74)
	95%CI Proportion	(82, 98)	(74, 93)	(78, 95)	(82, 92)	(63, 85)
Week 24 + 2 NRTIs	n (%)	52 (87)	51 (85)	53 (87)	156 (86)	46 (74)
	95%CI Proportion	(78, 95)	(76, 94)	(78, 95)	(81, 91)	(63, 85)
Week 48 + RPV	n (%)	48 (80)	48 (80)	53 (87)	149 (82)	44 (71)
	95%CI Proportion	(70, 90)	(70, 90)	(78, 95)	(77, 88)	(60, 82)
Week 96 + RPV	n (%)	41 (68)	45 (75)	51 (84)	137 (76)	39 (63)
	95%CI Proportion	(57,80)	(64,86)	(74, 93)	(69, 82)	(51, 75)

CAB was administered with 2 NRTIs through Week 24 (Induction Phase) of LATTE.

95% CIs are normal approximation confidence intervals.

Overall, the efficacy and safety data from the LATTE study, CAB exposure following LA administration, and limited drug-drug interaction potential, supported selection of the CAB 30 mg dose for once daily administration with the approved dose of RPV 25 mg once daily during the oral lead-in phase of studies with CAB LA and RPV LA. Select

plasma CAB PK parameters observed following oral administration with oral RPV, including following the oral lead-in for LATTE-2, are summarized in [Table 9](#).

Table 9 Summary of CAB Pharmacokinetic Parameters Following Repeat Oral Administration in HIV-Infected Subjects

Study	Once Daily Dose	Phase	Plasma CAB PK Parameter (Geometric mean [95%CI] (CVb%))				
			AUC(0- τ) ($\mu\text{g}\cdot\text{h}/\text{mL}$)	C _{max} ($\mu\text{g}/\text{mL}$)	C _{τ} or C ₀ ($\mu\text{g}/\text{mL}$)	T _{max} ^a (h)	AUC(0- τ) ($\mu\text{g}\cdot\text{h}/\text{mL}$)
LAI116482 (LATTE)	10 mg tab (n=14)	Induction Phase +2 NRTIs	45.7 [38.2, 54.6] (32)		2.77 [2.3, 3.3] (33)	1.35 ^b [1.2, 1.5] (45)	1.0 (0.9 – 8.0)
		Maintenance Phase +RPV 25 mg	---		---	1.34 ^c [1.1, 1.6] (58)	---
	30 mg tab (n=12)	Induction Phase +2 NRTIs	134 [110, 163] (32)		7.49 [6.3, 8.9] (28)	4.20 ^d [3.8, 4.7] (40)	2.0 (1.0 – 8.0)
		Maintenance Phase +RPV 25 mg	---		---	3.93 ^e [3.5, 4.4] (44)	---
	60 mg tab (2x30 mg) (n=9)	Induction Phase +2 NRTIs	195 [138, 277] (48)		11.5 [8.8, 15.0] (36)	7.93 ^f [7.2, 8.8] (39)	2.0 (1.0 – 8.0)
		Maintenance Phase +RPV 25 mg	---		---	8.22 ^g [7.4, 9.1] (37)	---
200056 LATTE-2 Day 1, predose	30 mg tab (n=246)	Induction Phase +2NRTIs	---	---	4.22 [4.0, 4.4] (43)]	---	

median (range)

n=57

n=50

n=53

n=51

n=55

n=49

